### 1.3. GLOSSARY OF ABBREVIATIONS

Abbreviation	Definition
AE	Adverse Event
AESI	Adverse Event of Special Interest
ALP	Alkaline Phosphatase
ALT	Alanine Aminotransferase
aPTT	Activated Partial Thromboplastin Time
AST	Aspartate Aminotransferase
ATC	Anatomical Therapeutic Classification
ATT	Anti-tetanus toxoid
CBC	Complete Blood Count
CE	Cerebral Edema
CI	Confidence Interval
CMP	Comprehensive Metabolic Panel
CNS	Central Nervous System
CR	Complete Response
CRF	Case Report Form
CT	Computed Tomography
CTCAE	Common Terminology Criteria for Adverse Events
DCR	Disease Control Rate
DLT	Dose Limiting Toxicity
DOR	Duration of Response
DSMB	Data and Safety Monitoring Board
EC	Exclusion Criteria
EGFR	Epidermal Growth Factor Receptor
EGFRvIII	Epidermal Growth Factor Receptor (variant III)
FLAIR	Fluid-Attenuated Inversion Recovery
GBM	Glioblastoma
GTR	Gross Total Resection
h	hour
IC	Inclusion Criteria
ICE	Intercurrent Events
ICF	Informed Consent Form
ICH	International Conference on Harmonization
IgG	Immunoglobulin G
irAE	Immune-related Adverse Event
iRANO	Immunotherapy Response Assessment in Neuro-Oncology
IV	Intravenous

kg	Kilogram
KPS	Karnofsky Performance Status
LS	Landmark Survival
LSQ	Lymphocyte Subset Quantitation
MedDRA	Medical Dictionary for Regulatory Activities
MRI	Magnetic Resonance Imaging
n	Participants
NANO	The Neurologic Assessment in Neuro-Oncology scale
ORR	Objective Radiographic Response/Objective Response Rate
OS	Overall Survival
PD	Progressive Disease
PP	Per-Protocol
PR	Partial Response
PRO	Patient-reported Outcome
PT	Preferred Term
PTE	Peritumoral Edema
PV	Poliovirus
RDI	Relative Dose Intensity
rGBM	Recurrent Glioblastoma
SAE	Serious Adverse Event
SAF	Safety Analysis Set
SD	Stable Disease
SOC	Standard of Care
TEAE	Treatment-Emergent Adverse Event
TESAE	Treatment-Emergent Serious Adverse Events
TERT	Telomerase Reverse Transcriptase
ULN	Upper Limit Normal
VEGF	Vascular Endothelial Growth Factor
WHO	World Health Organization
WHO-DD	WHO Data Dictionary

## 2. OBJECTIVES

Objective	Endpoint
Primary	
• Anti-tumor activity	• Objective response rate (ORR) • Duration of response (DOR)
• Safety/tolerability	• The frequency and severity of treatment-emergent adverse events (TEAEs) via Common Terminology Criteria for Adverse Events (CTCAE) v 5.0 for participants receiving lerapoltrev and at least one dose of pembrolizumab
Secondary	
• Anti-tumor activity	• Disease Control Rate (DCR)
• Survival	• Overall Survival (OS) • Landmark Survival (LS)

## 3. GENERAL STATISTICAL CONSIDERATIONS

### 3.1. SAMPLE SIZE AND POWER

In an analysis of the ongoing Phase 1 study of lerapoltrev in rGBM, an ORR of 11% was demonstrated (7/61 participants achieved a complete response (CR) or partial response (PR); data on file, Istari). With 30 participants planned to be treated in this study, there is a greater than 75% power to demonstrate a 20% or greater improvement in ORR (ORR > 31%, two-sided  $P < 0.05$ ).

### 3.2. HANDLING OF DATA

#### 3.2.1. Strata and Covariates

All analyses will be conducted without using strata.

#### 3.2.2. Multiple Testing and Comparisons

All analyses will be conducted without adjustments for multiple comparisons.

#### 3.2.3. Missing Data and Outliers

Every effort will be made to obtain required data at each scheduled evaluation from all participants who have been enrolled. In situations where it is not possible to obtain all data, it may be necessary to impute missing data. These situations are described below. Unless otherwise specified, all other missing data will not be imputed.

### **3.2.3.1. Missing Severity or Relationship for Adverse Events**

Adverse events (AEs) with missing severity will have the severity imputed as “Grade 3” for the AE tabulations. AEs with missing relationship to study drug will have the relationship imputed as ‘Definite’ for the AE tabulations if the AE started on or after catheter placement.

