## **7.2 Serious Adverse Events**

An SAE is any AE meeting the following criteria:

Death	An AE that results in death (note: death due to progression is not an AE/SAE but should be reported as noted in the eCRF completion guidelines).
-------	--

Life-threatening AE	An AE that places the participant, in the view of the Investigator, at immediate risk of death from the AE as it occurred (ie, does not include an AE that had it occurred in a more severe form, might have caused death).
Required or prolonged participant hospitalization	An AE that results in an initial participant hospitalization or prolongs an existing hospitalization of the participant. If a participant is hospitalized as part of the clinical use of the study treatment, the period of normal hospitalization will be based on the Investigator's judgement and experience. Hospitalizations longer than this period will be considered prolonged hospitalizations.
Persistent or significant disability/incapacity	An AE that results in a substantial disruption of a participant's ability to conduct normal life functions.
Congenital anomaly/birth defect	A congenital anomaly/birth defect that occurs in the offspring of a participant exposed to the study drug.
Important medical event	An AE that may not result in death, be life-threatening, or require hospitalization may be considered an SAE when, based upon appropriate medical judgment, the event may jeopardize the participant and may require medical or surgical intervention to prevent 1 of the outcomes listed above. Examples of such "important medical events" include allergic bronchospasm requiring intensive treatment in an emergency room or at home, blood dyscrasias or convulsions that do not result in participant hospitalization, or the development of drug dependency or drug abuse

SAEs must be reported by the Investigator to the Sponsor or designee within 24 h of discovery for all patients from the time of consent, while on study and for 30 days after 1) completion of study participation or 2) if patient is rendered off-study and in the follow-up period only. SAEs will be reported in the eCRF with instruction provided in the eCRF Completion Guidelines.

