### 5.8.1. Adverse Events

AEs will be mapped to a Medical Dictionary for Regulatory Activities (MedDRA) version 23.1 by system organ class and PT. If a participant experiences multiple events that map to a single PT, the greatest severity and strongest assessment of relation to a study drug will be assigned to the PT for the appropriate summaries. AE severity will be assessed according to the CTCAE version 5. If CTCAE grading does not exist for an AE, the severity of the AE will be graded as mild (1), moderate (2), severe (3), life-threatening (4), or fatal (5).

The number of participants for the following groups will be summarized by overall:

- Any TEAE
- Any TEAE related to a study drug or catheter with sub bullets for TEAEs related to catheter placement, lerapolturev or pembrolizumab
- Any TESAE
- Any TESAE related to a study drug or catheter with sub bullets for TESAEs related to catheter placement, lerapolturev or pembrolizumab
- Any DLTs
- Any AESIs for lerapolturev
- Any irAEs for pembrolizumab
- Any TEAEs leading to discontinuation of study treatment
- Any TEAE with grade  $\geq 3$
- Any TEAE with grade  $\geq 3$  related to study drug or catheter with sub bullets for TEAEs with grade  $\geq 3$  related to catheter placement, lerapolturev or pembrolizumab
- Any Grade 5 TEAEs
- Any Grade 5 TEAEs related to study drug or catheter with sub bullets for Grade 5 TEAEs related to catheter placement, lerapolturev or pembrolizumab

The occurrence of TEAEs and TEAEs related to study drug or catheter will be summarized by PT, system organ class, and severity. All AEs reported will be listed for individual participants showing both verbatim and PT. All AEs that occurred prior to catheter placement will be excluded from the tables but will be included in the listings.

Missing onset dates will be imputed as previously outlined in Section 3.2.3.2 as required to determine TEAEs.

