#### Safety

- 14.3.1.1 Overall Summary of Treatment-Emergent Adverse Events, Safety Set
- 14.3.1.2 Treatment-Emergent Adverse Events by System Organ Class, Preferred Term, and Greatest Severity, Safety Set
- 14.3.1.3 Treatment-Emergent Adverse Events by Preferred Term in Descending Frequency, Safety Set
- 14.3.1.4 Treatment-Emergent Adverse Events Related to Study Drug or Catheter by System Organ Class, Preferred Term, and Greatest Severity, Safety Set
- 14.3.1.5 Treatment-Emergent Adverse Events Related to Study Drug or Catheter by Preferred Term in Descending Frequency, Safety Set
- 14.3.1.6 Treatment-Emergent Serious Adverse Events by System Organ Class, Preferred Term and Greatest Severity, Safety Set
- 14.3.1.7 Treatment-Emergent Serious Adverse Events Related to Study Drug or Catheter by System Organ Class, Preferred Term, and Greatest Severity, Safety Set
- 14.3.1.8 Treatment-Emergent Dose Limiting Toxicities by System Organ Class, Preferred Term and Greatest Severity, Safety Set
- 14.3.1.9 Treatment-Emergent Adverse Events of Special Interest for Lerapoltrev by System Organ Class, Preferred Term, and Greatest Severity, Safety Set
- 14.3.1.10 Treatment-Emergent irAEs for Pembrolizumab by System Organ Class, Preferred Term, and Greatest Severity, Safety Set
- 14.3.1.11 Treatment-Emergent Adverse Events Leading to Discontinuation of Study Treatment by System Organ Class, Preferred Term, and Greatest Severity, Safety Set
- 14.3.4.1 Summary of Grade Shifts in Laboratory Abnormalities – Hematology, Safety Set
- 14.3.4.2 Summary of Grade Shifts in Laboratory Abnormalities – Chemistry, Pancreatic and Thyroid, Safety Set

- 14.3.4.3 Number of Participants with at Least One ALT, AST, or Total Bilirubin Above Upper Limit of the Normal Range Post-Baseline, Safety Set
- 14.3.4.4 Summary of Vital Signs by Visit, Safety Set
- 14.3.4.5 Summary of Karnofsky Performance Status by Visit, Safety Set
- 14.3.4.6 Summary of Neurologic Assessment in Neuro-Oncology Score by Visit, Safety Set

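### SAP 3.2.3.1 imputes Grade 3 for every missing AE severity, so an ungraded TEAE with outcome Death would be left out of the Grade 5 rows

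*SAP*

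**What the plan says.** SAP 3.2.3.1 reads: "Adverse events (AEs) with missing severity will have the severity imputed as" Grade 3 for the AE tables. It attaches no condition. The companion rule in the same section, for missing relationship, does have one: it applies only to events starting on or after catheter placement. That rule assigns Definite, the strongest attribution category in Protocol 7.1. SAP 3.2.3 rules out any further unstated imputation: "Unless otherwise specified, all other missing data will not be imputed".

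The imputed grade feeds two kinds of output:

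- **Overall AE summary (SAP 5.8.1).** This counts participants with "Any Grade 5 TEAEs", and with related Grade 5 TEAEs split by catheter placement, lerapolturev and pembrolizumab. It also has a row for "Any TEAE with grade" 3 or higher. Grade 4 has no row of its own.
- **Greatest-severity tables (SAP Section 10).** Table 14.3.1.2 is titled "Treatment-Emergent Adverse Events by System Organ Class, Preferred Term, and Greatest Severity, Safety Set". The same layout is planned for related TEAEs, serious TEAEs, DLTs, AESIs, irAEs and events leading to discontinuation.

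The protocol provides information that the rule does not use. Protocol 7.1 lists Death among the AE outcomes. The seriousness criteria in Protocol 7.2 begin with "An AE that results in death", followed by life-threatening events. For terms that CTCAE does not grade, Protocol 7.1 and SAP 5.8.1 use 4 for life-threatening and 5 for fatal.

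**The concern.** Grade 3 is a cautious value for an ungraded event that was really mild or moderate. For an event already recorded as fatal it works the other way: it puts the event below the grade that the rest of the record implies. The frequency and severity of TEAEs is the primary safety endpoint (SAP Section 2), and the Grade 5 rows are where AE deaths are attributed to the catheter, lerapolturev or pembrolizumab. As written, those rows could show fewer fatal events than the outcome field of the same database. In a small single-arm trial, one fatal event and none read very differently.

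**Working it through.** The plan states no figure on this point, so there is nothing to reproduce. The check applies the rule as written to simple cases and sizes the result.

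**Inputs.** The rule is from SAP 3.2.3.1, the rows from SAP 5.8.1, the tables from SAP Section 10 and the outcome categories from Protocol 7.1. The AE tables use the Safety Set, which is everyone with a catheter placed (SAP 4.2). About 30 participants were planned to receive both agents (SAP 1.1). SAP Section 6 says the full sample was not enrolled, and the actual number is not given.

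**Step 1: apply the rule.** Take three hypothetical participants, each with one ungraded TEAE: (A) outcome Death; (B) recorded as life-threatening, resolved; (C) neither. Compare the SAP rule with an outcome-based rule (A = 5, B = 4, C = 3).

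| Rule | Grade 3 | Grade 4 | Grade 5 | Grade 3 or higher |
|---|---|---|---|---|
| SAP 3.2.3.1 | 3 | 0 | 0 | 3 |
| Outcome-based | 1 | 1 | 1 | 3 |

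The Grade 3 or higher total is 3 under both rules. Only the split within it changes.

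**Step 2: find where the change shows.** Event A is lost from the Grade 5 row and, if related, from the related Grade 5 row and its attribution sub-rows. It also appears as Grade 3 in every greatest-severity table it enters. Event B changes only the greatest-severity tables.

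**Step 3: allow for other records.** Under SAP 5.8.1, where several events map to one preferred term, "the greatest severity and strongest assessment of relation to a study drug will be assigned to the PT". A second record in the same term graded 4 or 5 would therefore override the imputed 3. The misgrading shows only when no such record exists.

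**Step 4: size it.** One affected participant changes a Grade 5 percentage by 1/N:

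- N = 30 (illustrative): 1/30 = 3.3 points
- N = 25 (assumed): 1/25 = 4.0 points
- N = 20 (assumed): 1/20 = 5.0 points
- N = 15 (assumed): 1/15 = 6.7 points

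**The case against.** The best counter-argument is that the trigger is improbable and the deaths remain visible. Serious events must be reported within 24 hours (Protocol 7.2). Their narrative must give maximum severity, and the database closes only after queries are resolved (Protocol 8.3). Disposition reports death status and primary reason, with the date of death listed (SAP 5.1). The event stays in the any-TEAE and Grade 3 or higher counts, in the serious-TEAE count if reported as serious, and in the AE listing. Protocol Section 8 names Grade 3 or higher AEs as a key finding, and that count does not move. A treatment-related death or life-threatening event within the DLT window is a DLT through its seriousness, whatever its grade.

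All of this stands, and it limits the consequence. It does not make the rule right. A query may be closed by confirming that the data are unavailable (Protocol 8.3), and the imputation rule exists for exactly that remainder. The disposition summary cannot replace the Grade 5 rows: it has no split by attribution, and it includes deaths from progression, which Protocol 7.2 says are not AEs.

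A reader might infer more than the documents support:

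- **That fatal events vanish from the report.** They do not; only their grade is wrong.
- **That a Grade 4 row in the overall summary is understated.** There is no such row.
- **That a life-threatening seriousness criterion by itself fixes Grade 4.** The 4 and 5 wording is given only for terms without CTCAE grading, and no section shows a separate eCRF field for each criterion.
- **That confidence limits for the Grade 5 row would shift from those for 1/30 to those for 0/30.** SAP 5.8.1 plans no intervals for AE rows, and 30 is not the Safety Set denominator.

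**Conclusion.** The point holds in a limited form and is minor. The rule as written misgrades an ungraded TEAE with outcome Death, and neither document overrides it. The error is confined to the Grade 5 rows and the by-grade split; for life-threatening events it is confined to the by-grade split. One affected participant is worth 1/N of the Safety Set, with N unknown: 3.3 points at an illustrative 30, and 4.0 to 6.7 points if N is assumed to be 25 down to 15. This supposes that such a record survives cleaning and that the participant has no other record that preserves the higher grade. Nothing in the documents says that one does, so they do not support a conclusion that AE deaths have been under-reported.

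**What to change.** Replace the unconditional rule in SAP 3.2.3.1 with an ordered one for missing severity:

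1. Grade 5 if the AE outcome is Death or the event is recorded as resulting in death.
2. Otherwise Grade 4 if the event is recorded as life-threatening, provided the eCRF captures that criterion. State this in the SAP as an imputation convention, since the documents do not otherwise link the criterion to a grade.
3. Otherwise Grade 3, as now.

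Footnote the number of imputed grades in each affected table.

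The cost is one SAP sentence, one extra conditional in the code and the footnotes. The Grade 3 or higher totals do not change. The one dependency is the eCRF: if it does not hold the life-threatening criterion as a field, omit step 2 and keep step 1, which can rely on the AE outcome.

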### 7.1 Adverse Events

An AE is an untoward or medical occurrence associated with the use of study treatment (drug, biologic, or device) in clinical investigation participants, which does not necessarily have a causal relationship with the study treatment. An AE can therefore be any unfavorable and unintended symptom, sign, disease or condition, or test abnormality (although diagnosis should always be reported as the AE if known) regardless of the relationship to study treatment. AEs that do not meet the definition for an SAE are considered non-serious AEs. All AEs must be recorded in the patient's source documents and AE case report form.

AEs will be assessed according to the CTCAE v5. If CTCAE grading does not exist for an AE, the severity of the AE will be graded as mild (1), moderate (2), severe (3), life-threatening (4), or fatal (5).

All AEs will be followed until the outcome is determined by the Investigator as one of the following:

- Resolved
- Ongoing
- Chronic/Stable
- Death
- Unknown

Attribution of AEs/SAEs will be determined for each study intervention or concomitant medication/intervention, as applicable (ie, catheter placement, PVSRIPO, pembrolizumab, corticosteroids, bevacizumab).

Attribution of AEs will be indicated as follows:

- Definite: The AE is clearly related to the study drug(s)

- Probably: The AE is likely related to the study drug(s)
- Possible: The AE may be related to the study drug(s)
- Unlikely: The AE is doubtfully related to the study drug(s)
- Unrelated: The AE is clearly NOT related to the study drug(s)

Events that do not meet the definition of an AE include:

- Non-clinically significant (as assessed by the investigator), isolated, laboratory values, other than those noted in **Section 7.4**; see **Section 7.1.1** for assessing clinical significance of laboratory abnormalities for AE reporting.
- Medical or surgical procedures (eg, endoscopy, appendectomy).
  - Note: The condition that leads to the procedure can be an AE.
- Situations where an untoward medical occurrence did not occur (eg, social and/or convenience admission to a hospital).
- Anticipated day-to-day fluctuations of preexisting diseases/conditions present at baseline that do not worsen.
- Planned hospital admissions or surgical procedures for elective procedures or for an illness or disease that existed before the signing of the ICF or before the participant was enrolled in the study will not be captured as TEAEs/SAEs.

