### 1.1. **STUDY OVERVIEW**

This is an open-label, single-arm, non-randomized study characterizing the efficacy, safety, and tolerability of lerapolturev delivered via intratumoral infusion followed by pembrolizumab in patients with recurrent glioblastoma (rGBM). Approximately 30 eligible participants, 18 years of age or older, are planned to be enrolled and treated with lerapolturev and at least one dose of pembrolizumab in this study. The maximum planned duration of follow-up in this study is up to 24 months (104 weeks), and consists of the following treatments:

- Single lerapolturev infusion on Day 0
  - Note: retreatment with lerapolturev is allowed for qualifying participants who progress  $\geq$  6 months from initial lerapolturev infusion
- Pembrolizumab (200 mg intravenous (IV) infusion) initiated 14 days after lerapolturev infusion (up to 28 days, if necessary), given every 3 weeks, through Week 104 (23.5 months of treatment) or until immune-related AE (irAE) meeting criteria for dose interruption/discontinuation or confirmed progression (must consider clinical and radiographic assessments)

The study will occur in the following periods:

- Screening Period 1: Between 1 and 6 weeks prior to catheter placement
- Screening Period 2: Within 7 days prior to catheter placement
- Catheter Placement and Biopsy (if required) Period: Day 0
- Lerapolturev Infusion Period/Baseline: Single lerapolturev infusion on Day 0 or Day 1 (unless extension granted by Sponsor)
- Post-lerapolturev Infusion, Pembrolizumab Treatment and Follow-up Period: pembrolizumab starting at Week 2 (up to Week 4, max) and every 3 weeks thereafter, to a maximum of Week 104 (approximately 23.5 months maximum pembrolizumab treatment duration)

The study may be adapted or expanded in one or more larger cohorts of participants, in consultation with the Data and Safety Monitoring Board (DSMB), based on interim review and considering the totality of the study data.

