## 5.6. EXPOSURE

The number of participants who received study drug (lerapoltrev and pembrolizumab) and cumulative actual dose received will be summarized. The number of cycles of pembrolizumab administered will be summarized using 0 cycles, 1-5 cycles, > 5 cycles. The relative dose intensity (RDI) of pembrolizumab will be summarized using the percentage of drug a participant received compared to the planned amount of drug received, such that if the RDI is 100% the participant received all the planned doses. To calculate the RDI is (actual cumulative dose / planned cumulative dose) \* 100.

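### Missing AE relationship is imputed as Definite from catheter placement onward, with no condition that the drug in question had been given

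*SAP*

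**What the plan says.** The rule is in SAP 3.2.3.1. Where an AE has no recorded relationship to study drug, it assigns the strongest category, Definite. One clause limits this: "for the AE tabulations if the AE started on or after catheter placement". It names no drug and sets no other condition.

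Four other places decide what the rule does:

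- **What study drug means.** SAP 5.6 opens its exposure summary with "The number of participants who received study drug (lerapoltrev and pembrolizumab) and cumulative actual dose received will be summarized", so both agents are study drug there.
- **How relatedness is reported.** SAP 5.8.1 includes the line "Any TEAE related to a study drug or catheter with sub bullets for TEAEs related to catheter placement, lerapolturev or pembrolizumab". It repeats that split for serious TEAEs, TEAEs of grade 3 or higher, and grade 5 TEAEs.
- **How attribution is collected.** Protocol 7.1: "Attribution of AEs/SAEs will be determined for each study intervention or concomitant medication/intervention, as applicable".
- **When pembrolizumab starts.** SAP 1.1 has it "initiated 14 days after lerapolturev infusion (up to 28 days, if necessary").

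Lerapolturev in the SAP is the product that the protocol calls PVSRIPO.

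**The concern.** Imputing the worst case for a missing causality assessment is a normal, conservative choice as long as causation is possible. It is not possible before the first dose of a drug, or in a patient who never receives it. The SAP rule draws its line at catheter placement, which comes before both drugs and well before pembrolizumab.

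At stake are the per-agent lines of the overall AE summary. The trial has one arm, and SAP section 5 presents all tables for the overall population in one column. The split by catheter, lerapolturev and pembrolizumab is therefore the main place in the tables where toxicity added by pembrolizumab is separated from that of the virus and the procedure. A false entry in the pembrolizumab line would not stand out there. Protocol 8.4.5 planned a separate summary of patients given PVSRIPO alone, but the SAP's table list has none.

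**Working it through.** The plan gives no figure to reproduce. The check traces the rule through the SAP's own definitions, and then sizes one affected patient.

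**1. Is an AE before pembrolizumab inside the tables?** Yes. SAP 3.2.6 starts the TEAE period at catheter placement, and SAP 4.2 defines the safety set as enrolled participants with a catheter placed.

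**2. How long is the gap?**
- From infusion to first pembrolizumab: 14 to 28 days (SAP 1.1).
- From catheter placement to infusion: the same day or the next, extendable to 72 h, or 3 days, with Sponsor approval (Protocol 5.2.2).
- Longest gap from catheter placement to first pembrolizumab: 28 + 3 = 31 days.
- For a patient never given pembrolizumab, the gap is the whole TEAE period. Protocol 3.2 foresees such patients, and Protocol 4.5 replaces them but keeps them in follow-up.

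**3. A hypothetical record.** Suppose an AE starts on Day 5 after infusion, is recorded as Probable for lerapolturev, and has no pembrolizumab attribution. If pembrolizumab starts on Day 14, onset precedes it by 14 − 5 = 9 days. Onset is after catheter placement, so the rule sets the pembrolizumab relationship to Definite.
- Overall summary (SAP 5.8.1): the patient enters the pembrolizumab-related TEAE line, and the serious, grade 3 or higher, or grade 5 line if the event qualifies.
- Detailed tables 14.3.1.4, 14.3.1.5 and 14.3.1.7: whether the event counts as related does not change. These pool study drug and catheter, and the event is already related to lerapolturev.
- Within a preferred term, SAP 5.8.1 keeps the strongest relationship, so the imputed value would override a weaker recorded one.

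**4. The other reading of study drug.** SAP 3.2.3.2 speaks of a single study drug dose date, and SAP 3.2.6 sets Day 1 as the day study drug starts, which is the lerapolturev day. On that usage the rule covers lerapolturev only. It still fails in two situations:
- AEs between catheter placement and infusion, a gap of up to 72 h.
- Patients with a catheter who are never infused. Protocol 5.2.1 foresees catheter removal after a negative biopsy, and Protocol 7.1.3 foresees withdrawal for an AE between placement and infusion. They are affected if they count as enrolled under SAP 4.2; the SAP does not settle this for biopsy failures.

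On this reading, a missing pembrolizumab attribution has no stated rule at all, although SAP 5.8.1 tabulates it.

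**5. Is there an exemption?** None was found in either document. Analysing the safety set by treatment received (SAP 4.2) does not supply one, because the tables are pooled.

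**6. Size per patient.** The lines count participants, so a line moves only for a patient who is in it solely through the rule. With N patients the step is 100/N percentage points. At an assumed N = 30:
- 1 patient: 1/30 = 3.3 points.
- 3 patients: 3/30 = 10 points.

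The true N is not given. Replaced patients would raise it and make the step smaller. SAP section 6 says that the planned sample was not fully enrolled, which would make the step larger.

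**The case against.** **Missing values may be few.** Protocol 7.1 offers Unrelated as a category, the obvious entry for a drug not yet given, and the form may carry a not-applicable code. Protocol 8.3 has missing data queried and the database closed only after queries are resolved. Protocol 7.2 requires a causality assessment with the first report of an SAE, so a blank is least likely in the serious and grade 5 lines. This stands: whether the rule fires at all cannot be seen from the documents. It limits the size and does not make the rule correct.

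**Study drug may mean lerapolturev only.** The singular usage is real, so the plan is ambiguous. That narrows the error to the period before infusion and to patients never infused, but does not remove it.

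**The choice is conservative, and the listings allow a check.** AE listing 16.2.7.1 can be read against the infusion listings. That helps a careful reader, but the summary line would still be wrong.

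**Stronger readings to avoid.** A reader might infer that early AEs in general will be shown as definitely caused by pembrolizumab, or that a large share of patients will gain such an event. The documents support neither. The rule touches only missing attributions. The proposed tables show related events, with no row for Definite. Any share of patients would need an early AE rate and a rate of blanks, and neither is given. Nor do the documents show that edema events cluster before pembrolizumab: Protocol 6.2.2.1 places these neurologic changes within 12 months of infusion. DLTs and irAEs have their own definitions in SAP 3.2.6, and a blank pembrolizumab field is not shown to affect those tables.

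**Conclusion.** The concern holds as a defect in a stated rule. Whenever a relationship is missing for an AE that starts after catheter placement but before, or without, exposure to the drug, the SAP assigns a causal link that cannot exist. On the two-agent reading, which SAP 5.6 and 5.8.1 favour, the error goes to the pembrolizumab lines of the overall AE summary. On the lerapolturev-only reading it goes to the lerapolturev lines.

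Its overall size is unknown. About 3.3 percentage points per affected patient rests on two assumptions: a safety set of 30, and a patient who is not already in the line for another reason. A reader might infer that the primary safety endpoint is compromised. It is not: SAP section 2 defines it as the frequency and severity of TEAEs, and attribution does not enter. The change is worth making because it is cheap and the per-agent split has few other supports in a pooled single-arm table.

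**What to change.** Replace the relationship sentence in SAP 3.2.3.1 with a rule for each intervention:

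- Impute a missing relationship as Definite separately for catheter placement, lerapolturev and pembrolizumab, and only when AE onset is on or after first exposure to that intervention.
- Otherwise set the relationship to that intervention to Not Applicable and count it as unrelated.
- Report the number of imputed attributions for each intervention.

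SAP 3.2.3.2 must be aligned, because the new condition depends on onset date. That section completes a partial or missing onset date with the dose date of study drug and does not say which drug. State which dose date is used. If it is the lerapolturev date, an AE with no onset date would always fall before pembrolizumab and escape the pembrolizumab imputation. One remedy is to treat such an AE as after exposure unless the known parts of its date rule that out.

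The cost is an edit to two SAP subsections and a little more programming. The catheter and infusion data are already listed (16.2.5.1.1 to 16.2.5.1.3). The count becomes less conservative before exposure, and the worst-case imputation is kept in full after it.
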